#### 9.4 Deaths

The frequency (number and percentage) of subjects in the SAS who died and who died within 30 days after last dose of study treatment as well as the reason for death, will be tabulated:

- All deaths
- Deaths within 30 days after last dose of study treatment
- Reason for death

In addition, date and cause of death will be provided in individual participant data listing together with selected dosing information (study treatment received, date of first / last administration, dose) and will include the following information:

- AEs with fatal outcome (Listing of PTs of AEs with outcome=Fatal, as well as AEs of Grade 5)
- Flag for death within 30 days of last dose of study treatment.
- Flag for death related to COVID-19

#### 9.5 Clinical Laboratory Results

Clinical laboratory tests (serum chemistry and hematology) will be performed at Screening and each cycle Day 1 and 8, unless otherwise specified, as indicated in Section 10 of the protocol. Baseline laboratory measurements do not need to be repeated if screening measurements were performed within 3 days prior to Cycle 1 Day 1. All laboratory data will be converted to standardized conventional units for reporting purposes.

Hematology and chemistry evaluations which cannot be graded per CTCAE criteria will be summarized as counts and percentages of patients

Pfizer Inc. / Protocol: TTI-621-03/C4961003  
IQVIA Biotech (Confidential) Project # YXA42460

with shifts from baseline to worst on-treatment assessment  
(normal/low/high).

For hematology and chemistry evaluations which can be graded per CTCAE v5.0, the following summary table will be created:

- Shift summary of baseline CTCAE grade versus the worst on-treatment CTCAE grade (The highest CTCAE grade during the on-treatment period is considered as the worst grade [Grade 0, 1, 2, 3, or 4] for the summary)
- Shift summary from  $\leq$  Grade 2 at baseline to  $\geq$  Grade 3 postbaseline

An evaluation of Drug-Induced Serious Hepatotoxicity (eDISH) plot will also be created, with different symbols for different treatment groups, by graphically displaying:

- peak serum ALT(/ULN) vs peak total bilirubin (/ULN), including reference lines at ALT=3 $\times$ ULN and total bilirubin =2 $\times$ ULN.
- peak serum AST(/ULN) vs peak total bilirubin (/ULN), including reference lines at AST=3 $\times$ ULN and total bilirubin =2 $\times$ ULN .

## 9.6 Vital Signs

Vital signs (weight, systolic blood pressure, diastolic blood pressure) will be summarized with continuous descriptive statistics at Screening, on Cycle 1 Day 1 (assessed in 30-minute intervals), on all study treatment day 1 of each cycle, at EOT/Early Termination, and at Safety Follow up visit.

Vital Signs will be listed by patient and summarized by treatment and visit in the SAS.

## 9.7 ECOG

ECOG Performance Status will be assessed as described in the protocol Appendix A, at Screening, on Cycle 1 Day 1, on all study treatment day 1 of each cycle, at EOT/Early Termination, and at Safety Follow up visit.

*Time to first worsening of ECOG performance status* is defined as the time from the first PF-07901800 infusion (Cycle 1 Day 1) to the first date when a worsening from baseline (i.e., increase) in the ECOG assessment level is recorded in two consecutive assessments. Patients without a worsening event will be censored on the last date of ECOG assessments or the date of first study treatment, whichever is the later.

Pfizer Inc. / Protocol: TTI-621-03/C4961003  
IQVIA Biotech (Confidential) Project # YXA42460

The number of events and the number of censored patients will be summarized, and the median time to worsening event (reported in days), its 95% confidence interval, and the 25th and 75th percentiles on the time to event will be summarized using Brookmeyer-Crowley method.

## 9.8 Electrocardiograms

Supine position 12-lead ECGs will be performed at screening and reviewed locally at each visit.

Corrected QT, PR and QRS data will be collected on the ECG eCRF page. Data will be summarized using QTc.

The frequency (number and percentage) of participants with notable ECG values according to the following categories will be summarized:

- QTc increase from baseline >30 ms, >60 ms
- QTc > 450 ms, > 480 ms, > 500 ms
- PR  $\geq$  220 ms and increase from baseline  $\geq$  20 ms
- QRS  $\geq$  120 ms

Participants with notable ECG interval values and qualitative ECG abnormalities will be listed for each participant and time point and the corresponding notable values and abnormality findings will be included in the listings.

## 9.9 Transthoracic echocardiogram or Multigated Acquisition Scan

Patients must undergo a Transthoracic Echocardiogram (ECHO) or Multigated Acquisition (MUGA) Scan during the screening period, as well as in Cycle 5 day 1, Cycle 8 day 1 and in the Safety Follow-Up Visit, unless performed within previous 4 weeks. Left Ventricular Ejection Fraction (LEVF) and an overall interpretation (normal/abnormal) will be summarized by visit.

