### 9.3.3.1. Cardiac Toxicity Related to Doxorubicin Administration

Cardiotoxicity is a recognized risk of doxorubicin that increases with higher cumulative drug exposure. Cardiac monitoring is conducted by a combination of monitoring of clinical parameters, ECG and echocardiogram (ECHO) / multigated acquisition (MUGA) scan. ECG changes, arrhythmias, tachycardia, and/or chest pain should be managed according to clinical practice based on the specific findings.

Patients will undergo baseline LVEF determination by ECHO or MUGA scan. This evaluation may be repeated at any time during the study if clinically indicated. A decrease in LVEF of  $\geq$  10% and below the lower limit of normal, or an absolute decrease of 20%, or if the absolute LVEF decreases to or below 40%, doxorubicin will be discontinued. Doxorubicin should also be discontinued if the patient develops Grade  $\geq$  3 left ventricular systolic dysfunction (symptomatic congestive heart failure).

If doxorubicin is discontinued for the above changes in LVEF despite optimal prophylaxis, the patient may be eligible to continue on study with TTI-621 monotherapy after discussion with the Sponsor Medical Monitor, provided that the patient has completed at least four cycles of doxorubicin therapy, is receiving clinical benefit and meets guidelines for re-treatment with TTI-621.

The diagnostic method used at baseline for cardiovascular assessments (for example ECHO or MUGA scans) should be the same method used throughout the study, unless there is clinical or instrumental evidence that further investigations are needed.

The use of dexrazoxane to reduce the incidence and severity of cardiomyopathy due to doxorubicin administration in patients who have received a cumulative doxorubicin dose of 300 mg/m^2 and who will continue to receive doxorubicin is recommended and will be implemented in this study. As described in [Section 5.2.1.1](#), prophylaxis with dexrazoxane for cardiotoxicity must begin no later than with initiation of Cycle 5 when cumulative doxorubicin will have reached 300 mg/m^2. Do not administer dexrazoxane as a cardioprotectant at the initiation of doxorubicin treatment unless that is the standard of care at a particular institution.

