- o Detailed sample collection schedule provided in [Table 25](#)
- p Detailed sample collection schedule provided in [Table 27](#)
- q Detailed sample collection schedule provided in [Table 26](#)
- r Detailed sample collection schedule provided in [Table 27](#)
- s Assessed every 12 ± 2 weeks; telephone contact is acceptable
- t Does not need to be performed if previous assessment was within 72 previous hours
- u Prior to initiation of Cycle 3, Cycle 4 and Cycle 6; does not need to be performed if previous assessment was within seven days
- v Prior to initiation of every third cycle (Cycle 7, Cycle 10, Cycle 13, etc.); does not need to be performed if previous assessment was within seven days
- w Prior to initiation of Cycles 5 and 8; does not need to be performed if previous assessment was previous four weeks
- x Participants with an unresolved AE considered by the Investigator as possibly related to or associated with [REDACTED] will be asked to return for [REDACTED] blood sampling at approximately 3-month intervals (if feasible given the underlying disease) until the last follow-up of the AE up to a maximum of 12 months. [REDACTED]
- y Cycles 2, 3, 4, 5 only
- z Cycle 2 and Cycle 3 only
- aa Every second cycle (Cycle 7, Cycle 9, Cycle 11, etc.)
- bb Cycle 7 only
- CCI**  
[REDACTED]
- dd May be collected anytime within seven days prior to and 14 days after Cycle 3 Day 1; other times may be acceptable after consultation with Sponsor
- CCI**  
[REDACTED]
- ff To be performed 30 + five days after last administration of study treatment or before initiation of subsequent anti-cancer therapy, whichever occurs first

Table 25. Sample Collection Schedule for Analysis of CCI

Cycle	CCI
Day of Cycle	
Timepoint(s)	

CCI

Table 26. Sample Collection Schedule for Analysis of CCI

Cycle	CCI
Day of Cycle	
Timepoint	

CCI

Table 27. Sample Collection Schedule for Analysis of [REDACTED]

Screening	CCI	CCI
CCI		

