**Cycle 5 Day 1**

- Patient-reported QoL assessment
- Complete physical examination
- Vital signs (temperature, blood pressure, pulse rate, respiratory rate, weight, pulse oximetry)
- LVEF by transthoracic echocardiogram or MUGA (unless performed within previous 4 weeks)
- ECOG PS
- Serum chemistry (unless previous assessment was performed within previous 72 hours)
- Hematology (unless previous assessment was performed within previous 72 hours)
- Urine or serum pregnancy test (female patients of childbearing potential only; must be performed prior to treatment) Radiologic assessment of disease status (unless performed within previous 7 days)
- Administer doxorubicin with prophylaxis, including cardioprotectant (administration of cardioprotectant must be initiation no later than with Cycle 5, but may be initiated earlier per institutional standard of care)
- Administer TTI-621 with prophylaxis
- Adverse events
- Concomitant medications and procedures
- Blood collection for CCI [REDACTED]
- Blood collection for [REDACTED]
- Blood collection for [REDACTED]

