**Cycle 8 Day 1**

- LVEF by transthoracic echocardiogram or MUGA (unless performed within previous 4 weeks)

***Safety Follow-Up Visit (30 + 5 days after last administration of study treatment or before initiation of subsequent anti-cancer therapy, whichever occurs soonest)***

- Patient-reported QoL assessment
- Complete physical examination
- Vital signs (temperature, blood pressure, pulse rate, respiratory rate, weight, pulse oximetry)
- LVEF by transthoracic echocardiogram or MUGA (unless performed within previous 4 weeks with no abnormalities)
- ECOG PS
- Serum chemistry (unless performed within previous 72 hours)
- Hematology (unless performed within previous 72 hours)
- 12-lead ECG
- Urine or serum pregnancy test (female patients of childbearing potential only)
- Radiologic assessment of disease status (unless performed within previous 7 days)
- Adverse events
- Concomitant medications and procedures
- Blood collection for CCI [REDACTED]

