**12.3. Criteria for Evaluation****12.3.1. Safety**

All patients who receive at least dose of TTI-621 will be included in the safety analyses.

Adverse events, ECGs, LVEF assessments and laboratory data will be summarized and reviewed on an ongoing basis during the study. All adverse events, ECGs, LVEF assessments and safety laboratory abnormalities of potential clinical concern will be described. Safety data will be presented in tabular and/or graphical format and summarized descriptively by dose cohort and time where appropriate. Absolute value data and changes from baseline data will be summarized as appropriate.

AEs will be coded using the Medical Dictionary for Regulatory Activities (MedDRA) and severity of AEs and laboratory abnormalities will be graded using NCI CTCAE v5 as appropriate. Incidence tables of patients with AEs will be presented for all AEs by maximum severity, SAEs, AEs assessed as related to study drug and adverse events resulting in discontinuation of study drug.

For ECG analyses, the mean of the triplicate ECG parameters will be used as the observation for a patient at a nominal time point. Changes in ECG and laboratory measurements will be summarized.

Listings of all safety data sorted by dose cohort, patient and assessment date will be provided.

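### SAP 9.9 summarises LVEF by visit only, so a patient's lowest value may be absent from the table if a clinically triggered scan found it

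*SAP*

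**What the plan says.** SAP 9.9 is the only place where the readable SAP plans an LVEF summary. It requires a scan at screening, "as well as in Cycle 5 day 1, Cycle 8 day 1 and in the Safety Follow-Up Visit, unless performed within previous 4 weeks", and then says "Left Ventricular Ejection Fraction (LEVF) and an overall interpretation (normal/abnormal) will be summarized by visit".

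The protocol adds three things.

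- Section 9.3.3.1, on LVEF: "This evaluation may be repeated at any time during the study if clinically indicated".
- Table 24, footnote to the LVEF row: "Prior to initiation of Cycles 5 and 8; does not need to be performed if previous assessment was previous four weeks". The Section 11 lists for Cycle 5 Day 1 and Cycle 8 Day 1 carry the same exception.
- Section 11, Safety Follow-Up list, with a further condition: "LVEF by transthoracic echocardiogram or MUGA (unless performed within previous 4 weeks with no abnormalities".

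On reporting, Protocol 12.3.1 promises that "All adverse events, ECGs, LVEF assessments and safety laboratory abnormalities of potential clinical concern will be described", and that changes from baseline will be summarised as appropriate.

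The SAP treats other safety measures differently. For gradable laboratory tests, SAP 9.5 plans a "Shift summary of baseline CTCAE grade versus the worst on-treatment CTCAE grade". For ECGs, SAP 9.8 counts participants with notable values, including increases from baseline.

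**The concern.** Cumulative cardiac toxicity is the stated limit on doxorubicin (Protocol 3.4), and safety of the combination is a primary objective (Protocol 4.1). After baseline, LVEF is scheduled only three times. A scan prompted by symptoms between those visits is the one most likely to record a fall, yet the planned summary gives it no stated place. The same scan can also make the next visit's scan unnecessary.

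At stake is whether a reader of the LVEF table can see, by dose group, how low LVEF went and how many patients met the protocol's own LVEF criteria. Protocol 3.4 also cites mouse data in which CD47 blockade protected cardiac function under doxorubicin. A table that may omit the lowest values is a weak basis for any comment on that point.

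**Working it through.** The plan gives no LVEF figure to reproduce. The check is a comparison of texts plus a day count.

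**1. Where a triggered scan goes.** The only SAP rule that mentions unscheduled observations is 6.8.1. It applies when several observations fall at one specific visit, and it keeps the first, not the worst. It does not assign an off-visit scan to a visit. It also does not assign a scan that justified a waiver to the visit that was waived.

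**2. When a triggered scan can waive a scheduled one.** Inputs: six 21-day cycles, then 28-day cycles (SAP 4.1), and a four-week waiver taken as 28 days. Assumption: no delays.

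- Cycle 5 Day 1 = 1 + 4 × 21 = day 85
- Cycle 7 Day 1 = 1 + 6 × 21 = day 127
- Cycle 8 Day 1 = 127 + 28 = day 155

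| Scan waived | Days on which a triggered scan can waive it | Share of interval |
|---|---|---|
| Cycle 5 Day 1 | 57 to 84 (28 days) | 28/84 = 33% of days 1–84 |
| Cycle 8 Day 1 | 127 to 154 (28 days) | 28/70 = 40% of days 85–154 |
| Either | 56 days | 56/154 = 36% |

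On the other 154 − 56 = 98 days (64%) the next scheduled scan is still required if the patient remains on treatment. These are shares of calendar days, not probabilities that a scan is triggered.

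**3. The Safety Follow-Up waiver.** Three texts differ.

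| Source | Waiver at Safety Follow-Up |
|---|---|
| Protocol Table 24 | Footnote covers Cycles 5 and 8 only |
| Protocol Section 11 | Recent scan within four weeks and without abnormalities |
| SAP 9.9 | Recent scan within four weeks, no condition on its result |

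The difference matters most for a patient who stops before Cycle 5. Continuing on TTI-621 alone after an LVEF-related doxorubicin stop requires at least four completed doxorubicin cycles (Protocol 9.3.3.1). A patient stopped earlier will generally have no Cycle 5 or Cycle 8 row, so Safety Follow-Up is the only post-baseline row left.

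**4. What a by-visit summary can show.** The protocol's LVEF criteria mix falls from baseline with absolute levels. A visit summary of values and a normal/abnormal reading cannot give the number of patients who ever met them.

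**5. Which thresholds to count.** Protocol Table 18 and Section 9.3.3.1 do not agree. The absolute level is 45% in the first and 40% in the second. The wording of the two decline criteria also differs slightly (for example, greater than 10% against at least 10%).

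**The case against.** The best defence is that the signal is not lost. SAP 6.8 provides listings of all recorded data. SAP 7.2 summarises reasons for discontinuing each drug separately. SAP 9.3 tabulates events by maximum severity and events leading to permanent doxorubicin discontinuation. The Medical Monitor reviews echocardiogram and MUGA data throughout (Protocol 13.7). Protocol 12.3.1 promises a description, not a worst-value table. It can also be argued that a scan accepted in place of a scheduled one is naturally read as that visit's assessment.

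Much of this stands. The SAP nowhere says that such a scan is discarded, so the waiver point is an unstated rule rather than a stated exclusion. But adverse event and discontinuation tables show LVEF only when a fall was reported as an event or led to stopping. No cardiac category is among the adverse events of special interest, and listings do not give counts by dose group.

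A reader might go further and infer that patients with suspected cardiotoxicity vanish from the LVEF table. The documents do not support that: such patients keep their screening row and any other visit row, and what may be missing is a particular value. Nor does a triggered scan always cancel the next one. The Cycle 5 and Cycle 8 waiver is permissive and limited to four weeks, and under Protocol Section 11 an abnormal recent scan does not waive Safety Follow-Up.

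**Conclusion.** The point holds as a reporting gap of modest importance. SAP 9.9 has no worst-value, change-from-baseline or threshold summary for LVEF. It has no rule placing triggered or waiver-justifying scans, and its waiver wording departs from Protocol Section 11. A patient's lowest LVEF may therefore be absent from the only planned LVEF summary.

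The size of the effect cannot be stated. The 36% of days in which a waiver can operate assumes an undelayed calendar and says nothing about how often scans are triggered or LVEF falls. It would be an over-reading to say that the by-visit summaries will understate LVEF falls: they could, but no figure in the documents shows that they will. The response-rate analysis is unaffected.

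**What to change.** In SAP 9.9:

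1. Add, by treatment group, the minimum on-treatment LVEF and the largest decrease from baseline, using all scheduled and unscheduled scans. State the time window. SAP 6.4 ends the on-treatment period no later than 30 days after the last dose, while Safety Follow-Up may fall up to 35 days after it (30 + 5), so say whether that scan counts.
2. Count patients meeting each LVEF criterion printed in Protocol Table 18 and in Section 9.3.3.1, reporting each printed level. The sponsor must reconcile those two passages (45% against 40%).
3. State that a scan which justified a waiver is assigned to the waived visit.
4. Reconcile the SAP 9.9 waiver wording with Protocol Section 11 and Table 24.

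The cost is one extra descriptive table and a few sentences. This assumes that unscheduled scans are captured on the eCRF, which the documents do not show and the sponsor should confirm.

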Pfizer Inc. / Protocol: TTI-621-03/C4961003  
IQVIA Biotech (Confidential) Project # YXA42460

11.

CCI

[figure not shown]

CCI

Pfizer Inc. / Protocol: TTI-621-03/C4961003  
IQVIA Biotech (Confidential) Project # YXA42460

CCI

A large black rectangular box covers the majority of the page content, starting below the header and ending above the footer. The text "CCI" is visible in the top-left corner of this redacted area.
